## Exclusion criteria

- 1. Already received an influenza vaccine during the current influenza season
- 2. Not willing or able to get the flu vaccines being used in this study;
- 3. Previous hypersensitivity reaction to the study vaccines, or any vaccine, as reported by the subject
- 4. Received any non-influenza vaccine (e.g., Hepatitis B or other vaccine recommended for HCP) in the 4 weeks prior to the first study visit or plans to receive a vaccine in the 4 weeks following the first study visit
- 5. Currently participating in a study that involves an experimental agent (vaccine, drug, biologic, device, blood product, or medication), or has received an experimental agent within 1 month prior to enrollment in this study, or expects to receive an experimental agent during participation in this study.
- 6. Any condition or employment status that the potential participant or local study site principle investigator (PI) believes may interfere with successful completion of the study prior to December 2019, including being currently pregnant.

# Withdrawal criteria

In addition to exclusion criteria identified prior to enrollment, the following criteria will be used to identify withdrawal from the study:

- 1. Withdrawal of consent by participant for any reason
- 2. As deemed necessary by the principal investigator for noncompliance or other reasons
- 3. Lost to follow up defined as not returning for scheduled study visit 2
- 4. Receipt of influenza vaccine outside of the study and after enrollment

#### **6.3.2** Pre-screening and recruitment

The study will be open to HCP meeting the eligibility criteria at the two study sites. Prior to enrollment, study staff will identify potentially eligible HCP from SHIRI enrollment records. Pre-screening procedures may vary by enrollment facility. HCP will be recruited using a combination of methods that will be customized at each study site, including face-to-face meetings, phone calls, and printed material. Each site will describe the methods employed to recruit HCP potentially eligible for enrollment. All potential enrollees will be recorded in a recruitment log (**Appendix A. Recruitment Form**) in order to track invitations, acceptance, and refusal. All HCP who are interested in participation will have a screening and consent

appointment with a study physician, as required in Israel, in order to discuss the study purpose and procedures.

From the start of enrollment, sites will make efforts to recruit HCP from the priority Group One. In parallel HCP from the secondary Group Two will be recruited. If Group One recruitment goals cannot be reached, HCP from the Group One Supplemental will be targeted. A minimum target of 550 participants will be enrolled, including 275 at each site (see Section 9. Data Analysis). The target population of HCP will include 440 HCP from Group One, and 110 HCP from Group Two.

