Eligible HCP who were already vaccinated with Vaxigrip, the vaccine that is routinely available in Israel, at the time they are approached to join the study, will be invited to join the study as part of the Vaxigrip arm. Like randomized participants, participants who were vaccinated with Vaxigrip outside the study will complete a written consent form, an enrollment survey and grant permission for review of information collected during the SHIRI study, including vaccination status and immune response during the SHIRI study years. As part of the consent form, participants will record the estimated date that they received the vaccine, and the location, and will authorize study staff to verify the date of current-year Vaxigrip vaccination in the Clalit EMR and with the hospital vaccination staff. Participants will complete an enrollment survey and grant permission to include and integrate information collected during the SHIRI study into the current study's data, including health history, influenza vaccination history, and immune response to vaccination during the SHIRI study years. Blood specimens will be collected approximately 28 days after to evaluate immune responses to vaccination.

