#### 6.3.4 Randomization

Using the list of HCP consented to participate in the study, HCP will be randomized 1:1 to receive one 0.5 mL intramuscular dose of Flublok® Quadrivalent or Vaxigrip Quadrivalent. Randomization lists will be generated by the epidemiologist and data analyst using block randomization to ensure equal sample size in each group.

Randomization will be conducted after enrollment is completed. Randomization will occur separately for participants in Group One and Group Two.

Randomization will not occur for enrolled participants who were vaccinated with Vaxigrip outside of the study.

# 6.4 Study visit 1

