#### 9. DATA ANALYSIS

# 9.1 Power and Sample Size Considerations

To guide enrollment goals, we estimated the sample size required to do a two-sided test with a significance level of 0.05 and a power of 80%. The Food and Drug Administration criteria for demonstrating non-inferiority between IIV and a new vaccine requires comparisons of both the GMR and the SCR. We based expected values for the SCRs and GMRs comparing RIV3 and IIV3 on previously published estimates from prior vaccine immunogenicity trials. We assume that the SCR for IIV4 is  $\geq$ 40% and  $\geq$ 55% for RIV4, based on a clinical trial among adults <65 years demonstrating the SCR for IIV4 to range from 35% to 60% and RIV4 to range from 54%

to 63% against influenza A subtypes (seroconversion rates reported against influenza B viruses reflected trivalent vaccine formulations and were not included).  $^{23,32}$  We intend to have the power to show a 30% relative increase in SCR in the RIV arm compared to the IIV arm. Using the same assumptions and sample size would also provide adequate statistical power to detect a difference in post-vaccination GMT of  $\geq$ 2 fold between study arms if post-vaccination GMT value is  $\geq$ 20 for IIV4 and  $\geq$ 40 for RIV4. **Table 2** provides estimated sample sizes required for varying SCR and differences in SCR between study arms.

Based on prior experience enrolling participants at the two study sites, we will assume that 5% of participants will drop out before study visit 2.

Table 2. Sample size calculations to detect specified differences in SCR between RIV4 and IIV4 at approximately 28 days post-influenza vaccination

SCR at 28 days post- vaccination in IIV arm	Relative increase (%) in SCR in RIV arm compared to IIV arm at 28 days post-vaccination	IV arm Total enrollment for both study arms	
30%	10%	7526	
30%	20%	1926	
30%	30%	874	
40%	10%	4778	
40%	20%	1208	
40%	30%	540	
50%	10%	3130	
50%	20%	776	
50%	30%	340	
60%	10%	2032	
60%	20%	488	
60%	30%	206	

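### Recruitment targets count enrolled rather than randomised participants, so the minimum can be met with fewer randomised participants than Table 2 requires

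*Combined protocol and SAP*

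**What the plan says.** Section 6.3.2 gives the target and points to Section 9 for its basis: "A minimum target of 550 participants will be enrolled, including 275 at each site". It splits the 550 into 440 from Group One and 110 from Group Two. Section 6.1 gives a wider planning range of about 550 to 700 enrolled.

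Healthcare personnel who already received Vaxigrip outside the study are admitted by Section 1, Section 6.1 and inclusion criterion 3. Section 6.1 says they "will be invited to join the study as part of the Vaxigrip arm". Section 6.3.4 says: "Randomization will not occur for enrolled participants who were vaccinated with Vaxigrip outside of the study". No section limits their number, gives a separate target for randomised participants, or says that 550, 440 or 110 leaves them out. Exclusion criterion 1, in contrast, bars anyone already vaccinated in the current season.

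Section 9.1 sizes a "two-sided test with a significance level of 0.05 and a power of 80" percent, and states: "We intend to have the power to show a 30% relative increase in SCR in the RIV arm compared to the IIV arm". For 40% seroconversion on IIV4 and a 30% relative increase, Table 2 gives a total of 540 for both arms. On drop-out, Section 9.1 says "we will assume that 5% of participants will drop out before study visit 2". Sections 4.1 and 9.2 place the primary comparison in Group One, and Section 6.3.4 randomises Group One and Group Two separately.

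**The concern.** Table 2 describes two equal arms, and Section 6.3.4 provides the matching allocation: "HCP will be randomized 1:1 to receive one 0.5 mL intramuscular dose". The target meant to deliver that size is counted in a different unit. If enrolled has the same meaning in 6.3.2 as in 6.3.4, a non-randomised person fills a place in the target and adds nothing to the randomised comparison. The margin is small: 550 exceeds 540 by 10, so 11 such people (2% of 550) would leave 539 randomised.

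At stake is the power of the randomised comparison. A site could reach its 275 and close enrolment with the target met as worded, while the number randomised does not support the 80% on which Section 9.1 is built. The recruitment log in 6.3.2 tracks invitations, acceptances and refusals. As described, it does not track how many participants will be randomised.

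**Working it through.** **Inputs.** From Section 9.1: two-sided alpha 0.05, power 80%, IIV4 seroconversion 40%, a 30% relative increase (0.40 × 1.30 = 0.52), drop-out 5%. The alternative RIV4 rate is also from 9.1: "55% for RIV4, based on a clinical trial among adults <65 years". Allocation is 1:1 (6.3.4). Targets are 550 in total and 440 in Group One (6.3.2). The documents do not give the share vaccinated outside the study, so 0%, 10% and 20% are assumed to show a range.

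**Reproducing Table 2.** With pooled variance under the null, no continuity correction, and p̄ = (0.40 + 0.52)/2 = 0.46:

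n per arm = [1.960 × √(2 × 0.46 × 0.54) + 0.842 × √(0.40 × 0.60 + 0.52 × 0.48)]² / 0.12²
= (1.381 + 0.589)² / 0.0144 ≈ 269.6, rounded up to 270, so 540 in total.

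This matches the table, and the same formula reproduces all 12 rows. Table 2 therefore assumes equal arms and has no drop-out allowance. With 5% drop-out, 540 evaluable needs 540/0.95 = 568.4, that is 569 randomised.

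**Power for a given number randomised.** With N randomised, n = 0.95 × N / 2 evaluable per arm, and

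power = Φ{[0.12 × √n − 1.381] / 0.700}, where 0.700 = √(0.40 × 0.60 + 0.52 × 0.48).

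For Group One with none vaccinated outside: n = 0.95 × 440 / 2 = 209, 0.12 × √209 = 1.735, (1.735 − 1.381)/0.700 = 0.505, power 69.3%.

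For 40% against 55% the same formula, with difference 0.15 and p̄ = 0.475, needs 346 in total.

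| Target | Assumed share vaccinated outside | Randomised | Evaluable after 5% drop-out | Power, 40% v 52% | Power, 40% v 55% |
|---|---|---|---|---|---|
| Group One, 440 | 0% | 440 | 418 | 69.3% | 86.9% |
| Group One, 440 | 10% | 396 | 376 | 64.7% | 83.2% |
| Group One, 440 | 20% | 352 | 334 | 59.6% | 78.7% |
| All, 550 | 0% | 550 | 522 | 78.7% | 93.2% |
| All, 550 | 10% | 495 | 470 | 74.4% | 90.5% |
| All, 550 | 20% | 440 | 418 | 69.3% | 86.9% |

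The Group One rows describe the primary comparison. The rows for all 550 apply only if both groups are combined.

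**The case against.** Four points can be made for the plan.

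First, a reader might take 550 as the point at which recruitment stops. The documents do not say so. It is a minimum, inside a planned range of 550 to 700. At 700 enrolled, 160 could be vaccinated outside with 540 still randomised, or 131 with 569 randomised. Section 6.1 can also be read as randomising all 550 to 700, since 1:1 assignment follows in the same paragraph and the outside-vaccinated appear in the next one with no number attached. That reading is fair, but 6.3.4 does not use enrolled in that way, and nothing settles which meaning applies. For the same reason it is too strong to say that each outside-vaccinated person displaces a randomised one. That happens only if enrolment closes at the minimum while willing, unvaccinated personnel remain.

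Second, a reader might infer that the loss would go unnoticed. The documents do not support that. Outside vaccination is recorded at consent and randomisation uses a list of consented personnel, so the randomised count is known before any study vaccine is given. What stands is that 6.3.4 places randomisation after enrolment is complete, and no randomised target exists to check the count against.

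Third, Section 6.1 puts these people in the Vaxigrip arm, so the sponsor may have meant them to count. If 110 of 550 were pooled there (220 RIV4 against 330 IIV4), nominal power after drop-out would be 77.2%, against 78.7% with all 550 randomised. That comparison would no longer be fully randomised. Their baseline would be the SHIRI end-of-season sample (6.4.2) rather than a day-0 draw, while Section 9.2 relies on randomisation to remove confounding.

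Fourth, under 40% against 55%, power stays above 80% in most of the rows shown. This limits how serious the point is. However, Section 9.1 names the 30% relative increase as what it intends to have power for, so 540 is the right benchmark.

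**Conclusion.** The point holds as an ambiguity in the counting unit that bears on power. As worded, the plan can meet its minimum without randomising the 540 in Table 2. For the primary Group One comparison at 40% against 52% with 5% drop-out, power is 69% if all 440 are randomised, and 65% or 60% if 10% or 20% of them are not. At 40% against 55% it is 87%, 83% and 79%. These figures assume that only randomised participants are analysed. The 10% and 20% shares are illustrative; the true share could be smaller, since enrolment starts in July, ahead of the August–October vaccination period.

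It would be wrong to conclude that the word enrolled is the main cause of low power in Group One. The target of 440 is already below 540, and power there is 69% with nobody vaccinated outside. Even 550 randomised leaves 522 evaluable. The counting rule worsens an existing shortfall, and relabelling the targets would not by itself restore 80%.

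**What to change.** - In Sections 6.1 and 6.3.2, state 550–700, 440 and 110 as numbers randomised. Count personnel vaccinated outside the study separately, with their own line in the recruitment log.
- In Section 9.1, replace the implied 80% with the power for the number randomised in Group One after 5% drop-out, for both the 30% relative increase and 40% against 55%. For reference, 80% at 40% against 52% would need 569 randomised in Group One.
- Reconcile exclusion criterion 1 with Section 1, Section 6.1, inclusion criterion 3 and Section 6.3.4, so that it is clear whether personnel already vaccinated this season are eligible.

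The cost is a few sentences and one log entry. Recruitment may run slightly longer if outside-vaccinated personnel join, and the stated power becomes less favourable.

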# 6.3.3 Screening, consent and enrollment questionnaire

During the screening and consent appointment, the study physician will describe the study briefly and then conduct a brief interview to determine study eligibility (**Appendix B. Eligibility and Screening Form**).

The study physician will administer consent for eligible HCP interested in participating. The consent form will explain study details, risks, and benefits, and participating HCP will be asked to read, sign, and date the consent form (**Appendix C. Consent Form**). In addition to receiving a copy of the full consent form, all participants will receive a brief summary of the consent form and an outlined schedule of study visits. All potential study participants will be free to decide if they want to participate in the study. The consent will include permission to access medical records and link data from the previous study with data collected during the current study.

After consenting to the study, participants will complete a brief questionnaire about health status (self-perceived health status), hours and types of patient contact encountered as part of work duties (**Appendix D. Enrollment Questionnaire**).

#### 6.3.4 Randomization

Using the list of HCP consented to participate in the study, HCP will be randomized 1:1 to receive one 0.5 mL intramuscular dose of Flublok® Quadrivalent or Vaxigrip Quadrivalent. Randomization lists will be generated by the epidemiologist and data analyst using block randomization to ensure equal sample size in each group.

Randomization will be conducted after enrollment is completed. Randomization will occur separately for participants in Group One and Group Two.

Randomization will not occur for enrolled participants who were vaccinated with Vaxigrip outside of the study.

# 6.4 Study visit 1

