#### 1. PROJECT SUMMARY

Healthcare personnel (HCP) are believed to be at increased risk of influenza virus infection due to a higher rate of exposure compared with the general population. Close contact with patients may further result in transmission to patients. Vaccination is the most effective method of preventing influenza, but there is limited information on the effectiveness of influenza vaccines among HCP. Some studies have demonstrated reduced influenza vaccine immunogenicity and effectiveness among persons with a history of frequent influenza vaccination, emphasizing the need to examine influenza vaccine effects among HCP who may be frequently vaccinated or demonstrate a high baseline immune response to influenza viruses.

The primary objective of the study is to compare humoral immune responses to a single dose of recombinant hemagglutinin quadrivalent influenza vaccines (RIV4) or to standard egg-

based unadjuvanted quadrivalent influenza vaccines (IIV4) among  $HCP \ge 18$  years old who were vaccinated in the 2018-19 season with IIV4. The trial will be conducted at two hospital sites in Israel during the upcoming influenza season (2019-20) among HCP who were enrolled in the Study of Healthcare Personnel with Influenza and other Respiratory Viruses in Israel (SHIRI).

The study design is a randomized, single-blind, trial. During the study, eligible HCP at each site who consent to participate will be randomized 1:1 to receive a single dose of RIV4 (Flublok™ Quadrivalent by Sanofi, Inc., 45µg of HA per strain) versus a single dose of IIV4 (VaxigripTetra™ by Sanofi, Inc., 15µg of HA per strain). Participants will be blinded to the vaccine that they receive; study staff will not be blinded. Eligible HCP who report already having been vaccinated with Vaxigrip at the time they are approached to join the study will be eligible to participate. All randomized participants will have blood collected just prior to vaccination; all participants, including those who were vaccinated with Vaxigrip outside of the study, will have blood collected , approximately 28 days after to evaluate humoral immune responses to vaccination. Relative efficacy of single doses of study vaccines will be assessed by comparing immunologic responses to vaccination among participants receiving RIV4 and those receiving IIV4. In addition, the effect of prior vaccination in potentially modifying antibody immune responses to vaccine will be evaluated.

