#### 7. LABORATORY PROCEDURES

# 7.1 Blood Collection/Processing/Storage

After collection, blood specimens will be transported to the local laboratory for processing using standard procedures. Each tube will be labeled or barcode linked with the participant ID number, study visit number, and date of collection. Collected blood will be stored at 4°C immediately either by placing the sample on ice, in a 4°C refrigerator, or in a cooler with cold packs. Blood may be stored at 4°C for up to 18 hours. Sometime between 1 hour and 18 hours after collection, the blood collection tube will be centrifuged to separate the clotted blood from the serum and the serum removed to a clean tube labeled or barcode linked with the study participant ID number, study visit number, and date of collection. The clotted blood will be discarded. The serum will then be divided into approximately 8-10 aliquots of 1 mL/aliquot into labeled tubes. After aliquoting, the serum samples will be immediately stored at -20°C or colder.

Participant specimens will be stored indefinitely at a CDC-designated facility for future testing to evaluate aspects of respiratory infection and/or immune responses to influenza vaccine or influenza virus infection, as needed. Participants will also be asked if they would like to be contacted about future research studies related to this study.

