#### 8. VACCINE PRODUCT

Two vaccine products will be used in this trial: (1) the standard-dose quadrivalent inactivated influenza vaccine (expected to be Vaxigrip® Quadrivalent), and (2) Flublok® Quadrivalent. CDC or study sites will purchase vaccine. Both vaccines are inactivated influenza vaccines that are approved for use in adults aged ≥18 years in the United States. Vaxigrip Quadrivalent is licensed in Israel. Flublok is not licensed in Israel. Both vaccine products will contain vaccine strains representative of the four strains in the 2019-2020 northern hemisphere formulation.

Vaxigrip® Quadrivalent is a split-virus/subvirion vaccine manufactured by Sanofi Pasteur. It is formulated from influenza virus grown on embryonated chicken eggs. Vaccine virus is harvested, inactivated with formaldehyde, purified by zonal centrifugation using a sucrose gradient, split by Triton® X-100, and then further purified to a split-virus/subvirion form. The resulting vaccine suspension is clear and is available for use in adults as a prefilled single-dose 0.5mL syringe or a 5mL multi-dose vial; the vaccine is administered intramuscularly. Each dose is formulated to contain 15µg of HA per strain. Each 0.5mL dose of vaccine also contains sodium phosphate-buffered isotonic sodium chloride solution, up to 100µg of formaldehyde, and up to 250µg of octylphenol ethoxylate. Multi-dose vials also contain the preservatives,

thimerosal and mercury. The most common reactions occurring after vaccine administration in adults are pain at the injection site, myalgia, headache, and malaise. The vast majority of these reactions are mild to moderate, and severe reactions are very rare.

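### Section 6.3.4 does not name hospital as a randomisation stratum although Section 1 suggests it, and Section 9.2 has no site term; the sections should be reconciled and site pre-specified

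*Combined protocol and SAP*

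**What the plan says.** Section 6.3.4 starts from the list of consented HCP, allocates them 1:1 "using block randomization to ensure equal sample size in each group", and names one separation: "Randomization will occur separately for participants in Group One and Group Two". It does not mention hospital and gives no block size. It also fixes the timing: "Randomization will be conducted after enrollment is completed". Section 1 puts the allocation differently: "eligible HCP at each site who consent to participate will be randomized 1:1".

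Section 6.3.2 sets the targets: at least 550 participants, 275 per hospital, with 440 in Group One and 110 in Group Two. It does not say how each group divides between the hospitals. It allows pre-screening to vary by facility and states that "HCP will be recruited using a combination of methods that will be customized at each study site".

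In Section 9.2 the primary SCR comparison is a chi-square or Fisher exact test. GMT and GMR are compared by linear or generalised linear models, and titre thresholds by logistic regression. None of these names site. The text on secondary objectives mentions potential confounders in general terms and adjusts only where univariate analysis shows the arms to differ.

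Under Sections 6.1 and 6.3.4, HCP who had Vaxigrip outside the study join the Vaxigrip arm without being randomised.

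**The concern.** A programmer working from 6.3.4 alone would build two lists; a reader of Section 1 could expect four. If 6.3.4 is taken literally, hospital is controlled neither in the allocation nor in the analysis. If Section 1 governs, the allocation uses a stratum that 6.3.4 does not record and the analysis ignores.

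Three things are at stake. The arms can differ in hospital mix by chance, most of all in Group Two with about 55 per arm. Any variation between hospitals stays in the error term. And whether to adjust for hospital would be decided after looking at the arms.

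**Working it through.** **1. The plan's own sample size.** For Table 2, IIV4 SCR 40% with a 30% relative increase (52%), two-sided 0.05, 80% power, pooled variance and no continuity correction:

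n per arm = [1.96·√(2·0.46·0.54) + 0.842·√(0.40·0.60 + 0.52·0.48)]² / 0.12² = 269.6, rounded up to 270, so 540 in total.

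This matches Table 2, and the other eleven rows reproduce as well. Site does not enter the formula, so Table 2 is unaffected.

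**2. Chance imbalance without a site stratum.** Assumptions: each group splits evenly between the hospitals, the arms are equal, and list order is unrelated to hospital. The number x from one hospital in one arm is then hypergeometric, and the arm difference in hospital share is (2x − n)/n, where n is the arm size.

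- Group One (N = 440, n = 220): SD(x) = √(220·0.25·220/439) = 5.25. SD of the difference = 2·5.25/220 = 4.8 points; ×1.96 = ±9.4 points. P(at least 5 points) = 29%; P(at least 10 points) = 4.5%.
- Group Two (N = 110, n = 55): SD(x) = √(55·0.25·55/109) = 2.63. SD of the difference = 2·2.63/55 = 9.6 points; ×1.96 = ±18.8 points. P(at least 10 points) = 25%; P(at least 20 points) = 5.6%.

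**3. Shift in the GMT ratio.** The factor is 2^(d × share difference), where d is the hospital difference in log2 titre. The documents give no value for d; I assume 0.5 to 1 (about 1.4-fold to 2-fold).

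| Group | d = 0.5 | d = 1 |
|---|---|---|
| One | 2^0.047 = 1.03 | 2^0.094 = 1.07 |
| Two | 2^0.094 = 1.07 | 2^0.188 = 1.14 |

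These are 95% limits of a shift whose expectation is zero.

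**4. Shift in the SCR difference.** Assumed hospital SCR differences of 5, 10 and 20 points, multiplied by the 95% limits above, give about 0.5, 0.9 and 1.9 points in Group One and 0.9, 1.9 and 3.8 points in Group Two. The planned difference is 52 − 40 = 12 points.

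**5. Precision of titre models.** Share of variance due to hospital = 0.25·d²/SD². With an assumed SD of 1.5 to 2 log2, it runs from 0.25·0.25/4 = 1.6% to 0.25·1/2.25 = 11%. Removing it narrows confidence intervals by 1 − √(1 − 0.016) = 0.8% to 1 − √(1 − 0.111) = 5.7%.

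**6. Error rate and power for SCR.** Simulation of Group One (440, no dropout, 100,000 trials per scenario), null 40% v 40%, alternative 40% v 52%:

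| Hospital SCR difference (assumed) | Type I error, no site stratum, chi-square | Power, no site stratum, chi-square | Power, site lists and stratified test |
|---|---|---|---|
| 0 points | 4.9% | 71.5% | 71.6% |
| 10 points | 4.8% | 71.4% | 71.6% |
| 20 points | 4.8% | 71.6% | 73.0% |

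The largest gain from lists and test together is 73.0 − 71.6 = 1.4 points. The stratified test on unstratified lists gave 71.5%, 71.9% and 73.4%, so the gain comes from the analysis rather than the lists. With site lists but an unadjusted chi-square test, type I error at the 20-point difference was 4.4%, slightly conservative.

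**The case against.** The case on the other side is substantial. Section 6.3.4 does not say that group is the only stratum, and Section 1 is compatible with lists by hospital as well. That stands: the documents show an ambiguity, not a settled decision to ignore hospital.

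A reader might infer that the hospitals handle samples differently or use different vaccine lots. The documents do not support this. Section 7.1 says "blood specimens will be transported to the local laboratory for processing using standard procedures", with one set of storage limits for both hospitals. Section 8 says "CDC or study sites will purchase vaccine", which leaves the purchaser open and says nothing about lots. Section 6.1 gives a single vaccination window. Only pre-screening and recruitment are stated to vary. Differences in processing, lot or timing are possible but undocumented.

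Unstratified randomisation with an unadjusted test is valid, and if the consented list were sorted by hospital, the blocks would largely balance it anyway. Both points stand, though the plan gives neither list order nor block size.

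Finally, Section 9.2 does allow adjustment when the arms differ. This answers the concern only in part: the rule sits under the secondary objectives, does not name site, and depends on the data.

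**Conclusion.** The point holds as a low-cost improvement. Sections 1 and 6.3.4 need reconciling, and on either reading site is absent from the planned analysis.

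It would be tempting to conclude that the primary comparison is biased. Among randomised participants it is not: the expected shift is zero and simulated type I error without a site stratum is 4.8% to 4.9%. In Group One the effect is small against the planned 12-point SCR difference and the 2-fold GMT difference in Section 9.1. The power gain is at most about 1.5 points for lists and test together, and below 2 points in every simulated comparison. Group Two is more exposed but serves a secondary objective.

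The sizes rest on an even hospital split within each group, a list order unrelated to hospital, and assumed hospital differences in titre or SCR. None of these is given in the documents.

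**What to change.** - **Section 6.3.4:** state that block lists are generated by hospital within each group (four lists) and give the block size, so that the section agrees with Section 1. Because randomisation follows completed enrolment, every participant's hospital is already known. Hospital mix would then balance up to an incomplete block.
- **Section 9.2:** pre-specify site as a fixed effect in the linear and logistic models, and compare SCR with a site-stratified Cochran-Mantel-Haenszel test. For this factor, these replace the rule of adjusting only after a difference is found.
- **Participants vaccinated outside the study:** lists by hospital cannot balance people who are not randomised. For them, only the site term, or an analysis limited to randomised participants, deals with site; say which applies.

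The cost is two more lists from the same programme and one more model term. No extra participants, visits or samples are needed. If the lists already exist, record how they were made; the change to Section 9.2 can still be fixed before titres are compared by arm.
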